7.2.2 Exclusion Criteria

Participants who meet any of the following Exclusion Criteria may not be enrolled in the study:

- Participant with a medical history of severe cardiovascular or respiratory diseases (e.g., stroke, acute cardiovascular event, pulmonary thrombosis) in the last 12 months as self-reported.
- Participant with currently active cancer or history of cancer within the last 5 years as self-reported.
- Female participant who is pregnant or breast-feeding as self-reported.
- Participant is a current or former employee of the tobacco industry or their first-degree relatives (parent and child).
- Participant is an employee of PMI, [REDACTED] vendors, restaurant/event location employee or their first-degree relatives (parent and child).
- Specific to participants who are Non-Smokers:
Participant lives in a household with users of tobacco or nicotine-containing products, or is exposed to the use of tobacco or nicotine-containing products at the workplace.

7.3 Product Allocation and Blinding

7.3.1 Method of Grouping Participants According to Self Reported Product Use

In the Non-Exposure Events, participants will be either be in the IQOS Passive User Group, Cigarette Smoker Group, or Non-Smoker Group based on self-reported smoking status.

The same applies to the Exposure Events with the exception that IQOS Users will be allowed during the enrollment process to be in either the IQOS Active User Group, or the IQOS Passive User Group. The assignment to either of the two groups will be automatically done by the system with the IQOS Active User Group being filled first, to ensure the necessary sample size for the events.

7.3.2 Blinding

There is no blinding in this study.

8 DERIVED AND COMPUTED VARIABLES

For each timepoint (baseline urine void and last void), the change from Baseline will be calculated by subtracting the individual subject's Baseline value from the value at the end of the study. Mean change from Baseline is the mean of all individual subjects' change from Baseline values.

The percent change from Baseline will be calculated by subtracting the individual subject's Baseline value from the value at the end of the study and then dividing by the individual's Baseline value and multiplying by 100. Mean percent change from Baseline is the mean of all individual participant' percent change from Baseline values.

When the Baseline value is 0, the percent change from baseline will not be calculated and the number of such cases will be tabulated as "Not Calculated" in the descriptive summaries.

The geometric coefficient of variation (CV) will be calculated using the following formula:

$$CV = 100 \sqrt{e^{\text{var}} - 1}$$

where var = the variance from the log transformed data.

The geometric percent Relative Change (RC) from baseline will be calculated using the following formula:

$$RC = 100 * (\exp(\text{mean}(\ln(x) - \ln(\text{base}))) - 1)$$

where $\ln(x)$ are the natural logarithm of the individual values at the end of the study and $\ln(\text{base})$ are the natural logarithm of the individual baseline values.

8.1 Biomarkers of Exposure in Urine

The adjustment for creatinine for the urinary BoExp will be calculated as:

$$\text{BoExp (creatinine adjusted)} = \frac{\text{BoExp}}{\text{Creatinine}}$$

where the [] indicated concentrations measured from the spot urine collection.

8.2 Indoor Air Quality Measurements

This section describes how the IAQ variables are derived (Section 8.2.1) when used as covariates for the primary and secondary analysis of urinary BoExp. In addition, we describe the derivations (Section 8.2.2) for the IAQ variables when they are treated as endpoints.

8.2.1 Primary and Secondary Analysis of Urinary Biomarkers of Exposure

- Carbonyls: Acetaldehyde, Acrolein, Crotonaldehyde and Formaldehyde
 - At each event there are 3 machines where each collects 1 sample at 1 hour intervals over a 3 hour period.
 - All readings will be averaged over the 3 hour interval of an event and taken as one observation for all participants of the particular event.
- ISO measurement standards for ETS: 3-Ethenylpyridine (3-EP)
 - At each event there are 3 machines where each collects 2 samples at 3 hour intervals.
 - All readings from the 3 machines will be averaged and taken as one observation for all participants of the particular event.
- Real-time measurements of PM2.5 and PM10 suspended particles in air.
 - At each event there are 2 dedicated sensors measuring suspended particulate matter with a 1 minute interval monitoring.
 - For passively exposed participants we define the start time of exposure as the time of entry to the event room and end time of exposure as the time of collection of last urine sample. The exposure duration is defined as the start to end time of exposure for a participant. For each type of particulate matter (PM2.5 and PM10), the reading associated with a particular participant will be the average of all the readings from the 2 sensors depending on the participant's exposure duration.
 - For actively exposed participants we define the start time of exposure as the start time of first IQOS use and end time of exposure as the time of collection of last urine sample. The exposure duration is defined as the start to end time of exposure for a participant. For each type of particulate matter (PM2.5 and PM10), the reading associated with a particular participant will be the average of all the readings from the 2 sensors depending on the participant's exposure duration.

8.2.2 Secondary Analysis of Indoor Air Quality Measurements

- Carbonyls: Acetaldehyde, Acrolein, Crotonaldehyde and Formaldehyde
 - At each event there are 3 suitcases sampling each sample at 1 hour intervals over 3 hours.
 - Each of the 9 observations will be used as the observations for the associated event.
- ISO measurement standards for ETS: 3-Ethenylpyridine (3-EP) and Nicotine
 - At each event there are 3 suitcases sampling 2 replicate samples at the end of the 3 hour interval.
 - Each of the 6 observations will be used as the observations for the associated event.
- Tobacco Specific Nitrosamines: NNN and NNK
 - At each event there are 3 suitcases sampling 2 replicate samples at the end of the 3 hour interval.
 - Each of the 6 observations will be used as the observations for the associated event.

- Real-time measurements of PM2.5 and PM10 suspended particles in air.
 - At each event there are 2 sensors measuring the suspended particulate matter a 1 minute interval monitoring.
 - For each sensors, the average of all readings will be calculated from the start till end of the event. These averages will be used as observations for that particular event.

8.3 Questionnaires

All questionnaire data will be listed.

8.3.1 Self-reported tobacco and nicotine-containing product use

The self-reported tobacco and nicotine-containing product use questionnaire will be administered at enrollment within the CASI and during the check-in procedures of each event to confirm self-reported product use status.

The questions on Smoking History/Habits are self-administrated, to be answered by participants. No imputation for missing data will be performed.

The questions on product use are shown in Table 3.

Table 3. Self-Reported Tobacco and Nicotine Containing Tobacco Product Use

Question	Answer
1.1* Have you smoked at least 100 cigarettes in your ENTIRE LIFE?	Yes / No
1.2 In the past 12 months, did you smoke cigarettes?	Yes / No
1.3 In the past 30 days, did you smoke cigarettes...	Every day/Some days/Not at all
1.4 On how many of the past 30 days did you smoke cigarettes?	Numeric response, 2 digits
1.5 On average, on those days you smoked, how many cigarettes did you usually smoke each day?	Numeric response, 3 digits
2.1* Have you used at least 100 IQOS HeatSticks in your ENTIRE LIFE?	Yes / No

**Table 3. Self-Reported Tobacco and Nicotine Containing Tobacco Product Use**

	Question	Answer
2.2	In the past 12 months, did you use IQOS with HeatSticks ?	Yes / No
2.3	In the past 30 days, did you use IQOS with HeatSticks ?	Every day/Some days/Not at all
2.4	On how many of the past 30 days did you use IQOS with HeatSticks ?	Numeric response, 2 digits
2.5	On average, on those days you smoked, how many cigarettes did you use IQOS with HeatSticks ?	Numeric response, 3 digits
2.6	In the past 12 months, did you use a Heat-not-burn product other than IQOS with HeatSticks ?	Yes / No
2.7	In the past 30 days, did you use a Heat-not-burn product other than IQOS with HeatSticks ?	Every day/Some days/Not at all
2.8	On how many of the past 30 days did you use a Heat-not-burn product other than IQOS with HeatSticks ?	Numeric response, 2 digits
2.9	On average, on those days you smoked, how many cigarettes did you use a Heat-not-burn product other than IQOS with HeatSticks ?	Numeric response, 3 digits
3.1	In the past 12 months, did you use an e-cigarette?	Yes / No
3.2	In the past 30 days, did you use an e-cigarette?	Every day/Some days/Not at all
3.3	On how many of the past 30 days did you use an e-cigarette?	Numeric response, 2 digits
3.4	On average, on days you used, how many times did you usually use an e-cigarette each day?	Numeric response, 3 digits

**Table 3. Self-Reported Tobacco and Nicotine Containing Tobacco Product Use**

Question	Answer
4.1 In the past 12 months, did you use a Smokeless Tobacco Pipe?	Yes / No
4.2 In the past 30 days, did you use a Smokeless Tobacco Pipe?	Every day/Some days/Not at all
4.3 On how many of the past 30 days did you use a Smokeless Tobacco Pipe?	Numeric response, 2 digits
4.4 On average, on days you used, how many tobacco cartridges did you usually use each day?	Numeric response, 3 digits
5.1 In the past 12 months, did you use Smokeless Tobacco products?	Yes / No
5.2 In the past 30 days, did you use Smokeless Tobacco products?	Every day/Some days/Not at all
5.3 On how many of the past 30 days did you use Smokeless Tobacco products?	Numeric response, 2 digits
5.4 On average, on days you used, how many Smokeless Tobacco products did you use each day?	Numeric response, 3 digits
6.1 In the past 12 months, did you smoke Cigars/Pipes/Kiseru/Shisha?	Yes / No
6.2 In the past 30 days, did you smoke Cigars/Pipes/Kiseru/Shisha?	Every day/Some days/Not at all
6.3 On how many of the past 30 days did you smoke Cigars/Pipes/Kiseru/Shisha?	Numeric response, 2 digits
6.4 On average, on days you used, how many did you smoke Cigars/Pipes/Kiseru/Shisha?	Numeric response, 3 digits
7.1 In the past 12 months, did you use Nicotine Replacement Therapy?	Yes / No

**Table 3. Self-Reported Tobacco and Nicotine Containing Tobacco Product Use**

	Question	Answer
7.2	In the past 30 days, did you use Nicotine Replacement Therapy?	Every day/Some days/Not at all
7.3	On how many of the past 30 days did you use Nicotine Replacement Therapy?	Numeric response, 2 digits
7.4	On average, on days you used, how many Nicotine Replacement Therapy did you usually use each day?	Numeric response, 3 digits

*Only for CASI

8.3.2 Self-reported Health Outcomes and Events Questionnaire

A self-reported health outcomes questionnaire will be administered at enrollment within the CASI and during the check-in procedures of each event to confirm self-reported health status. The self-reported health outcomes and events questionnaire will focus on diagnoses of smoking-related disease and if the participant is pregnant or breastfeeding.

The questions on health outcomes are self-administrated, to be answered by participants. No imputation for missing data will be performed.

The questions on health outcomes in CASI are shown in Table 3.

Table 4. Self-Reported Health Outcomes and Events Questionnaire

	Question		Answer
*Question 1. Are you currently pregnant or breastfeeding?	1	Yes	
	2	No	
	3	Don't know/Not Sure	
Question 2. In the last 4 weeks, how has your overall physical health been?	1	Excellent	
	2	Very good	
	3	Good	
	4	Fair	
	5	Poor	
	6	I prefer not to say	

**Table 4. Self-Reported Health Outcomes and Events Questionnaire**

Question		Answer
Question 3. Have you ever been told by a medical professional that you have any of the following cardiovascular conditions or diseases?	1	Heart attack
	2	Stroke
	3	Angina (chest pain that happens suddenly and becomes worse over time)
	4	Unstable angina (chest pain that occurs seemingly without cause and has a sudden onset, sudden worsening)
	5	High blood pressure / hypertension
	6	Any other condition involving your heart or circulatory system
	7	None of the above
Question 3a Were any of the conditions you refer to above, diagnosed in the last 12 months?	1	Yes
	2	No
Question 4. Have you ever been told by a medical professional that you have any of the following respiratory conditions or diseases?	1	Chronic bronchitis
	2	Emphysema
	3	Chronic obstructive pulmonary disease (COPD)
	4	Apnoea (pauses in breathing during sleep)
	5	High blood pressure / hypertension
	6	Any other condition involving your lungs or respiratory system
	7	None of the above
Question 4a Were any of the conditions you refer to above, diagnosed in the last 12 months?	1	Yes
	2	No
Question 5 Have you ever been told by a medical professional that you have cancer in some parts of your body?	1	Yes
	2	No
Question 5a Was the cancer you refer to above, diagnosed in the last 5 years?	1	Yes
	2	No
	3	Don't know/Not sure

**Table 4. Self-Reported Health Outcomes and Events Questionnaire**

Question		Answer
Question 6 Have you ever been told by a medical professional that you have any of the following mental health disorders?	1	Anxiety disorder (including obsessive compulsive disorder)
	2	Depression
	3	Bipolar disorder
	4	Mood disorders (mood swings)
	5	Personality disorders (such as borderline personality or antisocial personality disorders)
	6	Other
	7	None of the above
Question 6a Were any of the conditions you refer to above, diagnosed in the last 12 months?	1	Yes
	2	No
	2	Don't know/Not sure

*For female participants only

8.4 Recording of IQOS Use

At each Exposure Event, the IQOS Active Users, will be provided with a personalized ashtray. IQOS *HeatSticks* that are used during the event will be collected in the ashtray and will be collected at approximately 1 hour intervals and recorded by the study personnel to evaluate the total number of *HeatSticks* used per participant during the Exposure Event.

For the analysis of the IQOS Active User Group, the number of *HeatSticks* used by a participant is defined as all *HeatSticks* used from the start of first use during priming until the end of the event.

8.5 Recording of Food and Alcohol Consumption

Overall Event-level consumption of beverages both alcoholic and non-alcoholic will be recorded hourly at each Event. The overall food consumption per food type will be recorded at each Event.

9 SAMPLE SIZE JUSTIFICATION

The sample size of a minimum of 169 participants in the Exposure Events and in the Non-Exposure Events is based on the expected change in exposure of a Non-Smoker when exposed passively to cigarette smoke, as documented in the literature. Variability of exposure levels and method variability were furthermore considered to estimate the sample size needed.

10 CHANGES FROM THE PROTOCOL SPECIFIED STATISTICAL ANALYSES

For the primary and secondary analysis, the random subject effect is removed as there are no repeated measures.

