### **Confidentiality Statement**

Data and information contained in this document are considered to constitute trade secrets and confidential commercial information, and the legal protections provided to such trade secrets and confidential information are hereby claimed under the provisions of applicable law. No part of this document may be publicly disclosed without the written consent of Philip Morris Products S.A.

---

Related to PMI\_RD\_WKI\_000759

Participants may attend a maximum of one Non-Exposure Event and one Exposure Event. Once participant confirms participation in the study, they are considered enrolled. No data will be recorded in the Study Database for the potential participants that do not consent to participate in the study. After consenting to participate in the study, participants can withdraw from the study at any time, but all data already provided by them, with the exception of their contact details, will be retained in the Study Database and analyzed as per the analysis plan. The contact details including personal information and personal identifiers will be kept separate from the study data.

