#### 4.1.3 Step 3: Exposure Events

This step comprises the Exposure Events which will occur in the same restaurant setting as the Non-Exposure Events in order to control for restaurant-related exposures that could confound study results. The first of the Exposure Events will occur within 4 weeks of the Non-Exposure Events and will replicate both the meal, beverages and restaurant dynamics (i.e. same location, air ventilation and table setting) of the Non-Exposure Event.

Exposure Event participants may or may not have attended a Non-Exposure Event, as this is not a study requirement. Participants attend the dinner event at no cost to themselves. These participants represent the same product use phenotypes as in the Non-Exposure Events, except that IQOS Users will be assigned for the Exposure Events to either a) IQOS Users who will use IQOS during the dinner event, or b) IQOS Users who agree not to use IQOS (or any nicotine or tobacco product) during the dinner event (see [Table 1](#)).

The Exposure Events will include a minimum of 169 passively exposure participants with the following product use phenotypes: 50% ( $\pm 5\%$ ) Non-Smokers, 25% ( $\pm 5\%$ ) IQOS Users who refrain from using any nicotine or tobacco product, and 25% ( $\pm 5\%$ ) Cigarette Smokers who refrain from using any nicotine or tobacco products.

---

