## 12.4 Primary Analysis

The primary endpoints will be the pre-event urinary BoExp and latest post two hour urinary BoExp observation. A linear mixed effects model with event type, IAQ, duration of exposure (time between pre-event collection and last post exposure collection), product use status and product use status and event type interaction will be modelled as fixed effects with a random subject effect. Other covariates or interactions terms may be added as needed. Appropriate contrasts will be constructed to determine the effect of passive exposure to IQOS aerosol during the Exposure Event on the mean change in levels of urinary BoExp to selected tobacco specific HPHCs together with the 95% confidence intervals (CIs). Other contrasts can be constructed to determine the change in urinary BoExp for subjects with other smoking status after passive exposure to IQOS usage

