3 INTRODUCTION

The purpose of the study is to assess the impact of passive IQOS exposure in Non-Smokers in a restaurant setting on the urinary levels of Biomarkers of Exposure (BoExp) to selected Harmful and Potentially Harmful Constituents (PHHCs) representative of Environmental Tobacco Smoke (ETS). And to compare the levels of BoExp in Non-Smokers from passive IQOS exposure with the levels of BoExp caused by background (Non-Exposure). Furthermore the impact of passive IQOS exposure was assessed in IQOS Users and Cigarette Smokers who did not use any nicotine or tobacco products during the Exposure Event.

The addition of IQOS Users who don't use IQOS, and Cigarette Smokers who did not use any nicotine or tobacco products during an Exposure Event, allows for the assessment of individuals with varying levels of BoExp to PHHCs in their personal lives, in order to assess whether there is any measurable additive exposure from IQOS. The study also evaluated Indoor Air Quality (IAQ) through the assessment of concentrations of IAQ markers in the air during the Exposure Events where IQOS was used and also during the Non-Exposure Events where there was no IQOS usage or Cigarette smoking allowed.

This Statistical Analysis Plan (SAP) describes the methodology and considerations of the planned analyses and lists the Tables, Figures and Listings (TFLs) for this study. A detailed description of the TFLs will be provided in a separate TFL shell document. Any changes to the TFL shell numbering or to the title of a TFL will not require an amendment to the SAP.

This SAP will be finalized prior to the lock of the clinical database. Any changes to the analyses described in this document or additional analyses performed to supplement the planned analyses, will be documented and described in the clinical study report (CSR).

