Table 1 below presents the four participant groups, measures of interest, and sample sizes, according to event type (Non-Exposure Event and Exposure Event).

**Table 1 Relative Exposure/participants groups, measures and sample sizes, according to event type (Non-Exposure vs Exposure)**

Variable	Non-Exposure Event	Exposure Event
Participants (group sizes can vary by \pm 5%)		
Sample Size required for Non-Exposure and Passive Exposure Group	N = 169	N = 169
• Group 1: Non-Smokers	50%	50% ²
• Group 2: Cigarette Smokers	25% ¹	25% ^{1,2}
• Group 3a: IQOS Passive Users	25% ¹	25% ^{1,2}
Total	100% participants in Non-Exposure Events	100% participant passively exposed in Exposure Events
• Group 3b: IQOS Active Users	n/a	20% of the total number of available 96 seats in the event location ³
Measures		
• Urine (void)	Before Start of the Event, as of ≥ 2 h after start of the Event until the end of the Event (last void analyzed only).	Before Start of the Event, as of ≥ 2 h after start of the Exposure until the end of the Event (last void analyzed only).
• Indoor Air Quality measures	For up to 3h prior to start of the Event; for 3h after the last participant has entered the Event for 1h.	For up to 3h prior to start of the Exposure; for 3h after the last participant has entered and has been exposed for 1h.

¹ Participants refrain from using any tobacco or nicotine products, including IQOS and/or cigarettes.

² Participants are allocated in these proportions after allowing for 20% of seats in each Exposure Event to Group 3b users.

³ Participants create the exposure to environmental tobacco aerosol through IQOS use.

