7.1.1 Step 1: Identification of Participants and Informed Consent: Screening and Enrollment

This step involves the identification of participants, and obtaining informed consent prior to the study (Non-Exposure or Exposure Events). Current adult IQOS Users and Cigarette Smokers will be identified and invited to participate through Philip Morris International's (PMI) product database. A

vendor will identify and recruit Non-Smokers from a panel of existing participants used for other research and survey purposes. Additionally, public advertisements might be used.

Potential candidates for participation in the study will be sent a link to a study website to provide information on study details and to complete a Computer-Assisted Self-Interview (CASI) system to assess eligibility and obtain informed consent. After completion of informed consent, the web system proceeds to the “screening domain” of the CASI which is the set of questions and questionnaires to evaluate the participants’ eligibility for participation (i.e., inclusion and exclusion criteria, eligible participants).

At the end of the “screening domain” eligible participants will be directed to the “enrollment domain” to confirm their participation in the study. Eligible participants will be presented with the available dates for the Non-Exposure and Exposure Events and asked to confirm their preferred dates for participation in maximum one Non-Exposure Event and maximum one Exposure Event. Once a participant confirms participation in the study, they are considered enrolled in the study.

No data will be recorded in the Study Database for the potential participants that do not consent to participate in the study. After consenting for participation in the study, participants can withdraw from the study at any time. The contact details of the participants, including personal information and personal identifiers will be kept separate from the study data. Participants will only be compensated for the Non-Exposure or Exposure Events they participated in.

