7.1.3 Step 3: Exposure Events

This step comprises the Exposure Events which will occur in the same restaurant setting as the Non-Exposure Events in order to control for restaurant-related exposures (i.e., location, air ventilation and table setting) that could confound study results. The first of the Exposure Events will occur within 4 weeks of the Non-Exposure Events. The Exposure Events will replicate the meal, beverages and restaurant dynamics of the Non-Exposure Event.

Exposure Event participants may or may not have attended a Non-Exposure Event. Participants attend the dinner Event at no cost to themselves. The participants who attend more than one event will represent the same product use phenotypes for both events, except the IQOS Users will be assigned for the Exposure Events to either a) an IQOS Active User, or b) an IQOS Passive User (see [Table 1](#)).

The Exposure Events will include a minimum of 169 passively exposed participants. During each Exposure Event a total of $20\% \pm 5\%$ of the available seats at the Event location will be allocated to IQOS Active Users (who use IQOS during the event). The remaining seats will consist of passively exposed participants with the following product use phenotypes: 50% ($\pm 5\%$) Non-Smokers, 25% ($\pm 5\%$) IQOS Passive Users who refrain from using any nicotine or tobacco product, and 25% ($\pm 5\%$) Cigarette Smokers who refrain from using any nicotine or tobacco products.

IQOS Active Users will enter the event location first and start using IQOS *ad-libitum* for 1h prior to the other participants (passive Exposure Group) entering the event location.

IAQ measurements will be sampled for up to 3h prior to the start of the Event and for 3h after the last participant was exposed for 1h. Urine specimens per person will be collected for analysis as follows:

The first urine sample will be collected prior to the start of the event. For the second urine sample, collection will only start with the first void after 2 hours of IQOS exposure to allow sufficient exposure to have occurred and therefore detection of BoExp in the urine. From the 2h time point onwards every subsequent void will be collected and the previous urine sample discarded with the last void collected ideally at the end of the 4h exposure period. Only the first and the last urine sample taken will be analyzed.

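### SAP section 10 drops the subject effect because there are no repeated measures, yet one person may attend both event types, so the post hoc Exposure vs Non-Exposure intervals may be the wrong width

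*SAP*

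**What the plan says.** Protocol 12.4 specifies a linear mixed model for the primary endpoints, with terms "modelled as fixed effects with a random subject effect". SAP section 10 lists one departure from the protocol: "For the primary and secondary analysis, the random subject effect is removed as there are no repeated measures". The PROC MIXED code in SAP 12.6.1.1, 14.1 and 14.5.1 accordingly has neither a RANDOM nor a REPEATED statement.

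Both documents provide for one person at two events:

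- Protocol synopsis, participant identification and enrollment: "Participants may attend a maximum of one Non-Exposure Event and one Exposure Event".
- Protocol 4.1.3: "Exposure Event participants may or may not have attended a Non-Exposure Event, as this is not a study requirement".
- Protocol 6.2.4 has its own heading for product use between events.
- SAP 7.1.1: at enrollment each person chooses "preferred dates for participation in maximum one Non-Exposure Event and maximum one Exposure Event".
- SAP 7.1.3: "The participants who attend more than one event will represent the same product use phenotypes for both events".

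The Compliant Exposure Set (SAP 11.2) admits anyone with valid samples from an event of either type. It does not restrict a person to one event.

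**The concern.** The dependent variable is the change from baseline within an event (SAP 12.6.1.1), so each attendance gives one row. This disposes of the pre/post repetition. It does not dispose of a Non-Smoker or Cigarette Smoker who attends both event types, or of an IQOS User who is passive at both. Such a person contributes two rows from the same body, and neither document says that there were no such people.

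The two rows lie on opposite sides of the comparison between event types. SAP section 3 names that comparison for Non-Smokers as a purpose of the study. SAP 14.1 acknowledges that the planned model did not make it. The post hoc ratios of geometric means in 14.1 (reported within Table 15.2.2.1.1) and 14.5.1 are therefore the only model-based comparisons of urinary biomarkers between event types. If the two changes in a person are correlated, the standard errors and 95% intervals of these ratios are wrong. They are too wide if the correlation is positive and too narrow if it is negative.

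**Working it through.** **Inputs from the documents.** The minimum is 169 non-exposed and 169 passively exposed participants (SAP 9). SAP Table 1 puts 20% of the "total number of available 96 seats in the event location" in the hands of active users at Exposure Events. SAP 12.6.2.1.1 counts two Non-Exposure and four Exposure Events.

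**Inputs that must be assumed.** *f* is the share of the smaller event-type group with a second row in the other group. *rho* is the correlation between one person's two adjusted log changes. Neither is in the documents.

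**Formula.** With n1 ≤ n2 rows in the two event types and m = f × n1 people in both,

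true variance of the log ratio = s² × [1/n1 + 1/n2 − 2 m rho/(n1 n2)].

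The model without a subject term reports s² × (1/n1 + 1/n2). Dividing,

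true/reported variance = 1 − 2 f n1 rho/(n1 + n2).

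Reported/true interval width is the reciprocal square root of this. Actual coverage is 2Φ(1.96 × reported/true width) − 1.

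**Two cases.**

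- Case A, equal groups as at the 169/169 minimum: the multiplier 2 n1/(n1 + n2) is 1.
- Case B, every seat filled once: 2 × 96 = 192 Non-Exposure places and 4 × 96 × 0.8 = 307.2 passive Exposure places. The multiplier is 384/499.2 = 0.769.

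| f | rho | Reported/true width, A | Reported/true width, B | Coverage, A | Coverage, B |
|---|---|---|---|---|---|
| 0.10 | 0.1 | 1.005 | 1.004 | 95.1% | 95.1% |
| 0.10 | 0.3 | 1.015 | 1.012 | 95.3% | 95.3% |
| 0.25 | 0.3 | 1.040 | 1.030 | 95.8% | 95.7% |
| 0.50 | 0.3 | 1.085 | 1.063 | 96.7% | 96.3% |
| 0.50 | 0.5 | 1.155 | 1.113 | 97.6% | 97.1% |
| 0.50 | −0.2 | 0.953 | 0.964 | 93.8% | 94.1% |

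Example, case A with f = 0.5 and rho = 0.5: 1 − 0.25 = 0.75, and 1/√0.75 = 1.155.

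**Does the formula survive the covariates?** An exact covariance calculation was run for the Non-Smoker ratio with baseline, sex, event type, product use, their interaction, duration and air-quality terms in the model. It set the covariates to their event-type means, as the text of 14.1 describes. True/reported standard errors for f = 0.5 and rho = 0.5 were 0.899 with 96 vs 154 Non-Smokers (formula 0.899) and 0.867 with 84 vs 84 (formula 0.866).

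**Planned within-event means.** Each person enters a given event type once, so the error does not arise in the same way. In the same calculation the standard error ratio for these means was 1.000 to 1.001 throughout.

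**Few dual attenders.** Five people in both groups of 84 Non-Smokers give f = 5/84 = 0.060. At rho = 0.5 the interval is 1.5% too wide.

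**The case against.** The strongest reply is that the stated reason is sound for what it was meant to cover. The protocol puts the same random subject effect into the Active Exposure Group model (12.5.1), where nobody can attend two Exposure Events. Its only role there is the pre/post pair, which suggests the same role in 12.4, and the change score replaces that pair. Section 10 also speaks of the primary and secondary analyses, whose planned estimates are barely touched. This largely stands: it explains the sentence and confines the error to section 14. It does not make the rows independent in the post hoc ratios, which reuse the same model.

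Second, dual attendance is permitted but not shown to have happened. IQOS Users fill the active group first, which reduces passive pairs among them, and adjustment for baseline removes much of the stable difference between people. Large values of both f and rho may therefore be unlikely. This also stands, and it is why the size is given only as a range.

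Third, correlation among people at the same event may matter more and push the other way. For 96 vs 154 Non-Smokers at two and four events, leaving out the air-quality terms, an assumed intraclass correlation of 0.01 adds 0.01 × (1/2 + 1/4) = 0.0075 to a variance factor of 1/96 + 1/154 = 0.0169. The true standard error is then about 1.2 times the reported one. That is a separate defect, and a subject term does not cure it. Where it is present, the net error in these intervals could be in either direction, so the figures above isolate the effect of dual attendance alone.

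Finally, no hypothesis is tested. That is correct, but in an estimation study the interval is the result.

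**Conclusion.** The concern holds, as a minor and conditional one. The reason in SAP section 10 is correct for the pre/post pair and for the Active Exposure Set. It is unsupported for people who are passive at both event types, whom the documents allow and the analysis set does not exclude. The consequence is limited to the intervals of the Exposure vs Non-Exposure ratios in 14.1 and 14.5.1. It is about 0.4 to 1.5% at 10% overlap with rho between 0.1 and 0.3, and 3 to 4% at 25% overlap with rho of 0.3. It exceeds 10% only when overlap and correlation are both substantial, for example one half and 0.5. With zero overlap or zero correlation there is no error. All sizes rest on assumed overlap and correlation, and on no further correlation among people at the same event.

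**What to change.** Reword section 10: the change score removes the pre/post repetition, and state whether any participant has two rows in the Compliant Exposure Set. Report that number by product use group, for example in Table 15.2.1.1.1 on event attendance, which is already listed. IQOS Users who are passive at one event and active at the other do not count.

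If the number is zero, give that as the reason and leave the models alone. If it is above zero, add `repeated event_type / subject=<participant ID> type=cs` to the models that produce the 14.1 and 14.5.1 ratios, with the participant ID in CLASS. Each person has at most one row per event type, so the structure fits, and it allows a negative correlation. Using it in 12.6.1.1 and 12.6.2.2 is for consistency only. Keep the removal for the Active Exposure Set.

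The cost is one sentence, one count and, if there is overlap, one line of code and a re-run. The drawback is that the correlation is poorly estimated from few pairs: its approximate standard error at zero correlation, 1/√(m − 1), is 0.50 with 5 pairs, 0.33 with 10 and 0.16 with 42. With only a handful the error is small too, so reporting the count alone would lose little.
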